13.2.2 Secondary Endpoints

Secondary endpoints of phase 2 portion of study are the following:

- Objective response rate (ORR)
- Event free survival defined as the interval between the date of first study treatment and the date of objective signs of disease recurrence, subsequent anti-leukemic therapy, or death, whichever is first reported EFS will be censored if entospletinib is discontinued for other reasons (such as drug is no longer available)
- Safety and tolerability of entospletinib in combination with obinutuzumab by AEs

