5.4 Duration of Treatment

In the absence of treatment delays due to adverse events, treatment will continue for at least 12 cycles (treatment with entospletinib may continue beyond 12 cycles, as noted elsewhere; obinutuzumab will be administered for 6 cycles) or until one of the criteria below applies.

- Disease progression
- Unacceptable adverse event(s),
- Intercurrent illness that prevents further administration of treatment,
- Participant decides to withdraw from the study, or
- Pregnancy, or
- General or specific changes in the participant's condition render the participant unacceptable for further treatment in the opinion of the treating physician.
- Closure of study by sponsor investigator or discontinuation of drug availability.

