5.5 Duration of Follow-up

Study participants will remain on study until disease progression, until study drug-related toxicities have resolved or are deemed irreversible by the sponsor-investigator (in discussion with a treating physician), whichever is later, or until the study is closed. If a study participant discontinues study treatment due to reasons other than progressive disease they will continue to be followed for disease assessments for 12 months after the End of Treatment visit, and for EFS until the end of study or study closure.

The expected duration of study will be 5 years, including enrollment (2 years), treatment (at least 1 year) and follow-up and EFS (2 years).

In the event of a study closure, participants currently receiving study drug will stop taking study drug and complete an abbreviated End of Treatment visit. Follow up and EFS will not continue after the End of Treatment visit.

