5.6 Criteria for Removal from Study

Participants will be removed from study under the following circumstances:

- Disease progression or start of new therapy of CLL/NHL
- Participant decides to withdraw from the study
- Pregnancy
- Patient is off treatment and has been on study for at least 4 years since the date of consent
- Study closure

The reason for study removal and the date the participant was removed must be documented in the study-specific case report form. Alternative care options will be discussed with the participant.

In the event of unusual or life-threatening complications, a lead PI ([name].) needs to be immediately notified at [contact].

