Treatment delays due to hematologic, non-hematologic and renal toxicities are permitted for up to 28 days from the end of a previous 28-day cycle. For longer delays, the study treatment will end (Section 5.5). In case of a treatment delay subsequent study assessment days will be adjusted accordingly. If a treatment delay occurs, both drugs (entospletinib and obinutuzumab) will be delayed.

For less severe toxicities not described above, holding one or both drugs and dose reductions are discouraged, but remain at the discretion of the treating physician.

Treatment with entospletinib and obinutuzumab will be discontinued if one of the following occurs despite dose modifications:

1. Second recurrence of grade 3-4 non-hematologic toxicities.
2. Second recurrence of grade 3-4 hematologic toxicities.
3. Treatment delay of >28 days from the end of a previous 28-day cycle.

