10.2 Treatment Period

Clinic visits will be performed every cycle on Day 1. Under certain circumstances (e.g., clinic holiday, inclement weather) Day 1 may be delayed by not more than 3 days or occur earlier than scheduled by not more than 3 days during cycles 2-12; Days 8 and 15 of Cycle 1 may be delayed by 1 day or occur 1 day early.

Clinical laboratory assessments are to be collected on D1 of each cycle visit, or \leq 48 hours before those visits, and the test results must be available and reviewed before obinutuzumab is given (C1-6). Screening assessment tests can be considered as Day -7 tests (start of treatment) if performed \leq 72 hours before the first dose of study treatment; otherwise, the required evaluations must be repeated within this timeframe.

On Day -7 and C1D1 all patients with CLL/SLL will provide samples for biomarker analysis.

After the initial 12 treatment cycles subjects in whom it is clinically safe to do so, are benefitting from entospletinib, and who desire to continue entospletinib monotherapy may continue entospletinib therapy beyond the initial twelve cycles, with approval from the treating physician and sponsor-investigator, until disease progression or removal from treatment (see Section 5.4).

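### Read literally, the EFS censoring clause in section 13.2.2 discards events that the protocol goes on collecting after entospletinib stops

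*Combined protocol and SAP*

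**What the plan says.** Section 13.2.2 measures EFS from first study treatment to the earliest of three events: objective recurrence, further anti-leukemic therapy, or death. It then adds: "EFS will be censored if entospletinib is discontinued for other reasons (such as drug is no longer available"). It gives no censoring date. Sections 1.2 and 10.4 define EFS by the same three events without this clause.

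Section 5.4 lists the reasons for stopping treatment. One is administrative: "Closure of study by sponsor investigator or discontinuation of drug availability". Others are clinical but are not EFS events: unacceptable adverse events, "Intercurrent illness that prevents further administration of treatment", and a change in condition that the treating physician considers incompatible with further treatment. Section 6.1 adds recurrent grade 3-4 toxicity and delays of more than 28 days, under the sentence "Treatment with entospletinib and obinutuzumab will be discontinued if one of the following occurs despite dose modifications". Section 10.2 says that suitable patients who wish to do so "may continue entospletinib therapy beyond the initial twelve cycles", so continuing is optional.

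For follow-up, section 5.5 covers the patient who "discontinues study treatment due to reasons other than progressive disease they will continue to be followed for disease assessments for 12 months", counted from the visit that closes treatment. The same section separately extends EFS follow-up beyond those 12 months, in these words: "and for EFS until the end of study or study closure". Section 10.4 and Table 10 schedule EFS checks every 3 months in the first year after End of Treatment and every 6 months after that. At study closure, EFS collection ends.

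Section 13.4.2 summarises EFS descriptively by Kaplan-Meier. Section 13.4.3 adds EFS estimates by biomarker and by prior kinase inhibitor.

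**The concern.** The open-ended wording makes loss of drug supply one instance of a wider class. Any entospletinib stop that is not itself an EFS event falls under it, including stops for toxicity or decline. Sections 5.5 and 10.4 and Table 10 keep observing those same patients for EFS. An analyst who follows section 13.2.2 would drop their later recurrences, new therapies and deaths; one who follows sections 1.2 and 10.4 would count them. Both could claim to follow the protocol, and the curves could differ.

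Kaplan-Meier treats a censored patient as having the same later risk as those still being followed. If patients who stop do worse, the censored curve is too high. If they do better, it is too low. If stopping is unrelated to risk, there is no bias, but observed events are thrown away in a study of about 20 patients.

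**Working it through.** **The plan's own figure.** There is none. The documents give no EFS rate, event count, stopping rate or risk after stopping. Only the sample sizes, n = 17 and 20, come from the plan (section 13.5). What follows is illustration.

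**Assumed inputs.** Exponential event times with an on-drug median of 24 months, so L = ln 2 / 24 = 0.02888 per month. Event-free stopping of p = 10% or 30% per 12 months, so d = -ln(1 - p)/12 = 0.00878 or 0.02972. Hazard after stopping h × L, with h = 0.5, 1, 2 or 3. Time t = 24 months.

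**Step 1, bias.**
- Censoring at stop: exp(-L t) = 50.0%.
- Counting all events: S = exp(-(L+d)t) + d·exp(-hLt)·[1 - exp(-(L+d-hL)t)]/(L+d-hL).
- Example, p = 30%, h = 2: 0.2450 + 0.02972 × 0.25 × 23.76 = 0.422.

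| h | All events, p = 10% | All events, p = 30% | Censored minus all-event (points) |
|---|---|---|---|
| 0.5 | 51.9% | 55.6% | -1.9 / -5.6 |
| 1 | 50.0% | 50.0% | 0 / 0 |
| 2 | 47.3% | 42.2% | +2.7 / +7.8 |
| 3 | 45.5% | 37.2% | +4.5 / +12.8 |

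Across medians of 12, 18, 24 and 36 months, h = 2 to 3 gives +2.2 to +12.8 points and h = 0.5 gives -1.6 to -6.4.

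**Step 2, precision (24-month median).** Large-sample Kaplan-Meier variance with this censoring is (S²/n)·L·[exp((L+d)t) - 1]/(L+d), with S = 0.5.
- p = 10%: SE 11.9 points (n = 20), 12.9 (n = 17).
- p = 30%: SE 13.8 (n = 20), 14.9 (n = 17).
- No such censoring: √(0.25/20) = 11.2 and √(0.25/17) = 12.1.

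The upward shifts in the table are therefore about 0.2 to 0.9 SE.

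**Step 3, events lost at equal risk (h = 1, 20 patients).** All events by 24 months: 20 × 0.5 = 10.0. Counted: 20·L/(L+d)·[1 - exp(-(L+d)t)] = 9.13 (p = 10%) or 7.44 (p = 30%). Uncounted: 0.9 or 2.6.

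**Step 4, only if stops after 12 cycles count as discontinuation.** Stop time a = (12 × 28 + 7)/30.4375 = 11.3 months. Suppose a fraction q of event-free patients stops then and nobody stops otherwise.
- Censored: 20·q·exp(-La) = 3.6 (q = 0.25) or 7.2 (q = 0.5).
- Uncounted at equal risk: that number × [1 - exp(-L(24-a))] = 1.1 or 2.2 of 10.0.
- Variance: (S²/n)·{[exp(La) - 1] + [exp(Lt) - exp(La)]/(1-q)}. SE at n = 20: 12.3 or 14.2, against 11.2.

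**Cross-check with inputs borrowed from the background.** A simulation (n = 17, 36-month horizon) used either 70.1% progression-free at 24 weeks (section 2.2.4; exponential median about 10.8 months) or a 26.7-month median (section 2.3.2.2). It took 20.2% stopping for toxicity or decline by cycle 12, the withdrawal rate in the obinutuzumab-chlorambucil arm. At equal risk, the clause cut counted events from 15.3 to 13.2 and from 10.3 to 8.6, a loss of 14% to 16%. With h = 2 to 3 after those stops, 24-month EFS was overstated by about 3 to 7 points. These are different settings and treatments, so the result shows only that the order of size is not peculiar to the first set of assumptions.

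**The case against.** **Only administrative stops were meant.** This is the strongest reply. The one example is drug supply, and section 5.4 puts that in the same bullet as study closure. At closure EFS collection ends, so censoring is unavoidable and correct. On that reading the clause agrees with section 5.5. It may well be the intention, but the text does not limit itself to it, and the remedy would still be to say so.

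**Finishing 12 cycles is completion, not discontinuation.** The opening of section 10.0 sets the planned cycles against discontinuation for a section 5.4 reason, and section 5.4 does not list completion as such a reason. This stands in part. A reader might infer that every event-free stop after cycle 12 is censored; the documents do not settle that, so step 4 is one possible reading.

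**Other passages.** A reader might also see a conflict with section 10.3 (all subjects enter the EFS analysis), section 13.7 (all available data used where possible) or the removal criterion in section 5.6, "Patient is off treatment and has been on study for at least 4 years since the date of consent". None is a real contradiction. A censored patient is still in a Kaplan-Meier analysis, section 13.7 concerns missing data and is qualified, and section 5.6 says nothing about which events count. The conflict is with sections 5.5 and 10.4 and Table 10, and with the definitions in sections 1.2 and 10.4.

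**The size is assumed.** True. The largest shift, 12.8 points, needs 30% stopping a year and a threefold hazard. At a 12-month median the same inputs give 9.0. At the 10.8-month median implied by the entospletinib figure, h = 2 to 3 gives about 2 to 8.

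**Conclusion.** The concern holds as a defect of wording with consequences for the analysis. Read literally, section 13.2.2 does not count EFS events that sections 5.5 and 10.4 and Table 10 arrange to collect, and it gives no censoring date. Toxicity, illness and decline stops are within its wording; stops at or after cycle 12 are within it only on one reading.

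Under the assumed inputs, the 24-month estimate moves by roughly 2 to 13 points upward or 2 to 6 downward, below one standard error at n = 17 to 20. At equal risk there is no bias, only lost events and a wider interval.

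A reader might infer that the plan inflates EFS, or that the trial's efficacy conclusion is in doubt. The documents support neither. The direction depends on risk after stopping, which they do not give. EFS has no hypothesis or threshold, and the rule of at least 7 CRs in 17 patients does not use it. What is affected is the descriptive secondary EFS and the exploratory EFS subgroup estimates. Censoring at study closure or withdrawal of consent is not in question. The change should be made, but it is not critical to the trial.

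**What to change.** In section 13.2.2, replace the clause with a statement that the three EFS events already defined there count whether or not entospletinib has been discontinued. Event-free patients are censored at their last disease assessment, including at study closure, withdrawal of consent or loss to follow-up. The event definition itself stays as it is.

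If the sponsor wants censoring at loss of drug supply, limit the clause to that reason and state the censoring date. Use the same definition in sections 1.2 and 10.4.

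The cost is a sentence in section 13.2.2 and matching text in the other two sections. No visits are added, because sections 5.5, 10.3 and 10.4 already schedule the follow-up. The EFS estimate may move in either direction.

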13.2.3 Exploratory Endpoints

- Peripheral blood B-cell depletion and recovery
- Pharmacodynamics effects of *in vivo* administration of entospletinib on NF κ B activation and expression of anti-apoptotic proteins in CLL cells.
- Association of established biomarkers (chromosomal abnormalities, immunoglobulin heavy chain [*IGHV*] mutational status, p53 mutational status) with response (ORR and EFS) to ENTO in combination with obinutuzumab in patients with relapsed/refractory CLL

13.3 Analysis Population

Safety analysis set includes all patients who consent and take at least one dose of study drug, regardless of how long they stay on study drug. The end of treatment and early termination visit (see schedule) includes an evaluation of response at that visit. Reason(s) for going off study will be collected on every patient.

The dose-determining set (DDS) consists of a subset of patients in the safety analysis set who either meet the following minimum exposure criterion and have sufficient safety evaluations, during the first 1 cycle of dosing (including the run-in phase) or discontinue earlier due to DLT.

The efficacy-evaluable population will include all intent-to-treat (ITT) subjects who received at least 1 dose of study medication. Per protocol population will include all intent-to-treat (ITT) patients who completed 1 cycle of study treatment. The ITT subjects will include all subjects who are consented and enrolled in the Phase 2 Portion of the study.

13.4 Statistical Analysis Plan

Demographic and baseline data will be summarized descriptively by phase and dose level. For continuous variables, descriptive statistics will include the mean, standard deviation (or standard error), median, range, and interquartile range. For categorical variables, descriptive statistics will include the number and percent.

13.4.1 Analysis of Primary Endpoints

The MTD will be determined according to 3+3 dose escalation design using the dose determining set. Adverse events will be graded and categorized according to the CTCAE v4.03. All adverse events will be tabulated and summarized by major organ category, grade, anticipation, and drug attribution. SAE specific incidence and exact 95% confidence interval will be provided where appropriate.

The CR will be computed and presented together with the exact 95% confidence interval (CI), using the method of Clopper and Pearson. A null hypothesis of a 20% CR will be rejected if at least 7 of 17 patients achieve a CR and a treatment arm will not be considered further if this threshold is not reached.

13.4.2 Analysis of Secondary Endpoints

- Overall response rate (ORR) will be summarized with 95% confidence intervals.
- Event free survival (EFS) will be summarized descriptively using the Kaplan-Meier estimate.
- Safety and tolerability of entospletinib in combination with obinutuzumab by AEs
Safety data will be summarized for the safety population separately for phase 1 and phase 2 portions by dose level. All AEs will be coded by system organ class, MedDRA preferred term, and severity grade using NCI CTCAE (v 4.03).

13.4.3 Analysis of Exploratory Endpoints

Pharmacokinetic parameters including peak and trough levels will be determined by non-compartmental method(s) using the pharmacokinetic profile of entospletinib and obinutuzumab. EFS and ORR by status of complete response will be summarized using descriptive statistics.

We hypothesize that subjects with tumors demonstrating unfavorable chromosomal abnormalities (i.e., del(17p) or del(11q)), unmutated immunoglobulin heavy chain [*IGHV*], or mutations in *TP53* will be associated with decreased ORR and EFS compared with subjects without these biomarkers when treated with entospletinib and obinutuzumab combination. Point and interval estimates of ORR and EFS by biomarker outcome will be provided for each patient subgroup.

Similarly, we hypothesize that patients who have previously received targeted therapy with kinase inhibitors (ibrutinib, idelalisib or investigational inhibitors of BTK, PI3K) will demonstrate worse outcomes. Point and interval estimates of ORR and EFS will be provided separately for such patients.

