2.2.4. Clinical Trials

Entospletinib has been administered to 540 subjects (328 healthy subjects, 7 subjects with rheumatoid arthritis, 76 subjects with CLL, and 155 subjects with NHL) in 11 Phase 1 and Phase 2 clinical studies. Single agent efficacy has been demonstrated with entospletinib in subjects with relapsed or refractory hematologic malignancies (CLL/SLL, MCL, DLBCL, FL, LPL, or MZL). PFS rates are 70.1% (95% CI: 51.3%, 82.7%) at 24 weeks for subjects with CLL (n=41) and 50.2% (95% CI: 29.3%, 67.9%) at 24 weeks in subjects with FL (n=41). The most common AEs (observed in \geq 15% of subjects) in hematology patients receiving entospletinib alone (n = 186) include fatigue (52.5%), nausea (43.3%), diarrhea (40.8%), decreased appetite (27.1%), constipation (23.8%); cough (22.5.0%), dizziness (19.6%), pyrexia (18.8%), vomiting (18.3%), headache (17.9%), dyspnea (16.7%), insomnia (15.8%), dehydration (15.0%), and upper respiratory infection (15.0%). Thirty four subjects (14.2%) reported an AE of rash.

Entospletinib is expected to produce *asymptomatic and transient elevations of indirect bilirubin* due to inhibition of UGT1A1. In studies of subjects with hematologic malignancies, 9 of 252 subjects had elevations of direct bilirubin with the onset of elevation ranging from Day 8 to 85, except for 1 subject at Day 169. Bilirubin elevations were generally self-limited and did not result in discontinuation of entospletinib.

In a phase 2, open label study evaluating the efficacy, safety, tolerability, and pharmacodynamics of the combination of entospletinib and idelalisib administered twice daily over multiple 28 day cycles to subjects with relapsed or refractory lymphoid malignancies, pneumonitis was reported in 12 of 66 subjects (18.2%), leading to the discontinuation of further evaluation of this combination [18]. All subjects were to receive treatment with entospletinib and idelalisib twice daily under fasted conditions and the study allowed intra-subject dose escalations every 2 weeks. Of the 12 pneumonitis AEs, 11 (91.7%) were SAEs, 7 were Grade 3, 2 were Grade 4, and 2 were Grade 5. The protocol was amended to allow a subset of subjects to receive monotherapy with entospletinib after a 14 to 28 day washout period with no subsequent cases of pneumonitis reported. Pneumonitis has *not* been identified as a risk with entospletinib monotherapy.

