- **Echocardiogram (ECHO):** will be performed at screening if clinically indicated. LVEF will be measured per institutional standard. Echocardiograms will be repeated as clinically indicated.
- **Computerized Tomography Scan (CT):** neck, chest, abdomen and pelvis are required with contrast. If contrast cannot be used for clinical reasons, a CT without contrast will be acceptable. Cheson criteria should be used to read each scan.

CT scans performed within 30 days of the first study treatment are acceptable for baseline assessment. Additional CT scans will be obtained at C4D1, C7D1, C10D1 (or \leq 72 h prior), C18D1 and C24D1, if appropriate, at the end of treatment visit, at 6 and 12 months after the end of treatment visit (\pm 7 days) and as clinically indicated thereafter. CT scanning may be performed at any point where it is suspected that disease progression has occurred between scheduled assessments.

NOTE: In subjects with NHL (FL, MZL, MZL) – PET-CT scans *may* be performed in place of CT scans at screening, during the study and at follow-up. However, the same modality should be used for each individual patient during the study.

NOTE: In subjects with LPL, CT scans on C4D1, C10D1 and during follow-up will be performed only if lymphadenopathy is present at screening, or if new lymphadenopathy develops during scheduled CT scans on C7D1 or the EOT visit.

- **Adverse Event Assessments:** Toxicities and adverse experiences will be assessed at each visit using the NCI Common Toxicity Criteria for Adverse Events 4.0. Adverse events will be reported and recorded as indicated in section 7 of this protocol.
http://ctep.cancer.gov/protocolDevelopment/electronic_applications/ctc.htm
- **Bone Marrow Aspirate and Biopsy** (optional at screening unless ANC<1,000/mm³ or platelets<50,000/mm³; optional at the end of treatment): will include cytogenetics and FISH, per institutional standards. Bone marrow biopsy performed within 6 months prior to the first dose of study treatment is acceptable.

Bone marrow biopsy should also be performed between 1 and 3 months at any time CR is suspected (e.g., C7D1, C10D1, C18D1, C24D1). An End-of-Treatment visit bone marrow biopsy will be performed between 1 and 3 months after the End of Treatment visit, unless study closure occurs. However, if CR is confirmed by bone marrow biopsy after C7D1, an EOT biopsy will not be performed.

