- **Biomarker Blood Samples:** see protocol section 9 – Correlative studies for detailed description of collection
- **Overall Response Assessment:** performed at C7D1, EOT and during the first year following EOT to coincide with CT scans at 6 and 12 months post EOT.
-
- **Event-Free Survival (EFS) Assessment:** performed every 3 months during the Follow-up period, and every 6 months after the Follow-up period unless study closure is in effect. EFS is defined as the date of objective signs of disease recurrence, subsequent anti-leukemic therapy, or death, whichever is first reported.

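### EFS by complete-response status is counted from first dose with no landmark, so the exploratory summary favours CR patients by construction; ORR by CR status is redundant

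*Combined protocol and SAP*

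**What the plan says.** Section 13.4.3 (Analysis of Exploratory Endpoints) states: "EFS and ORR by status of complete response will be summarized using descriptive statistics". It gives no date at which CR status is fixed, no landmark and no time-dependent method; nor does any other section.

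The clock for EFS is set in section 13.2.2: "Event free survival defined as the interval between the date of first study treatment" and the first event. First treatment is the Day -7 entospletinib dose. Section 13.4.2 adds only that "Event free survival (EFS) will be summarized descriptively using the Kaplan-Meier estimate", and section 13.2.2 that "EFS will be censored if entospletinib is discontinued for other reasons".

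CR status is acquired during follow-up. Section 11.2.1 makes a marrow examination part of CR. Section 10.4 says "Bone marrow biopsy should also be performed between 1 and 3 months at any time CR is suspected", with C7D1, C10D1, C18D1 and C24D1 as examples; note C to Table 9 places the confirming marrow one to three months after the corresponding CT. Section 10.4 has overall response "performed at C7D1, EOT and during the first year following EOT", while Table 9 ties a response assessment to each CT, including the one at C4D1.

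Section 1.2 defines ORR to include CR, CRi, PR and nPR.

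**The concern.** A patient can enter the CR group only by remaining event-free until CR is confirmed. A patient who progresses, starts other therapy or dies before then can only be non-CR. The time from first dose to confirmation is therefore event-free by construction in one group, while the other group absorbs all the early events. This is immortal time. Kaplan-Meier curves, medians or fixed-time EFS rates shown side by side carry the bias as fully as a test would.

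CR is the phase II primary endpoint, and this is the only planned summary that relates CR to how long benefit lasts. A reader of the results would naturally take it as evidence on that question, and as planned it cannot separate a real association from the artefact.

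The ORR half of the sentence has a simpler problem. CR is a component of ORR, so ORR among CR patients is 100% whatever the data.

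**Working it through.** The plan states no figure for EFS or ORR by CR status, so there is nothing to reproduce.

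**When CR can be confirmed (days after first dose)**
- C4D1: 7 + 3×28 = 91 (week 13). One to three months later is about weeks 17 to 26.
- C7D1: 7 + 6×28 = 175 (week 25). One to three months later is about weeks 29 to 38, ending near day 175 + 91 = 266.
- C10D1: 7 + 9×28 = 259 (week 37), with confirmation later still.
- End-of-treatment visit after 12 cycles: 7 + 12×28 + 56 = 399 (week 57).

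**Assumptions**
- EFS is exponential. The low level is anchored to section 2.2.4, where single-agent "PFS rates are 70.1% (95% CI: 51.3%, 82.7%) at 24 weeks for subjects with CLL (n=41"): λ = −ln(0.701)/24 = 0.01480 per week, median ln 2/λ = 46.8 weeks. The high level is an assumed median of 156 weeks.
- CR is assigned at random to a share q = 0.5 of patients event-free at confirmation week τ, so CR has no true effect.
- Follow-up is three years (156.5 weeks), in line with section 5.7.

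**Formulas**, with S(t) = exp(−λt), H = 156.5 and I(a,b) = [S(a) − S(b)]/λ:
- CR events = q[S(τ) − S(H)]; CR time = q[τS(τ) + I(τ,H)].
- Non-CR events = 1 − S(H) − CR events; non-CR time = I(0,H) − CR time.

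**Worked case: median 46.8 weeks, τ = 29**
- S(29) = 0.651, S(H) = 0.0986, I(0,H) = 60.90, I(29,H) = 37.32.
- CR: events 0.5×(0.651 − 0.0986) = 0.276; time 0.5×(29×0.651 + 37.32) = 28.10; rate 0.00983.
- Non-CR: events 0.9014 − 0.276 = 0.625; time 60.90 − 28.10 = 32.80; rate 0.01906.
- Ratio 0.00983/0.01906 = 0.52. Median EFS is 76 weeks (CR) against 28 weeks (non-CR).
- Counting from week 29 in patients event-free then: CR rate 0.276/(0.5×37.32) = 0.0148 = λ. The non-CR rate is the same, so the ratio is 1.0.

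**Spurious CR to non-CR rate ratio, q = 0.5**

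| Median EFS | τ = week 17 | τ = week 29 | τ = week 38 |
|---|---|---|---|
| 46.8 weeks | 0.64 | 0.52 | 0.45 |
| 78 weeks | 0.70 | 0.58 | 0.51 |
| 104 weeks | 0.73 | 0.60 | 0.53 |
| 156 weeks | 0.75 | 0.63 | 0.55 |

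A landmark at τ gives 1.0 in every cell. If CR status were fixed only at the end-of-treatment visit (week 57), the same formulas give 0.36 to 0.43.

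**ORR by CR status.** In CR patients it is 1 by definition. In non-CR patients it is (ORR − CR)/(1 − CR). With the section 13.5 benchmark of 77.3% and 20.7%, this is 0.566/0.793 = 71%. Both rows follow from the overall ORR and CR rates.

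**The case against.** The strongest reply is that little hangs on this sentence. The plan speaks of a descriptive summary. It has no test, hazard ratio or stated hypothesis here, whereas the biomarker and prior-kinase-inhibitor subgroups in the same section do carry hypotheses and interval estimates. EFS by CR status is not listed in sections 1.3 or 13.2.3. The phase II decision rests on the CR count alone. All of this stands and sets the priority, but it does not remove the bias, because a descriptive display has it too.

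Second, the timing is not fixed by the documents. The time points in section 10.4 are examples, and Table 9 has a CT and response assessment at C4D1, although its marrow row is blank for cycles 2 to 6. Weeks 29 to 38 is therefore one reading, which is why the range starts at week 17.

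Third, the only EFS anchor is single-agent PFS applied to a combination. A single headline ratio near 0.5 would rest on that pessimistic level; longer EFS shrinks the artefact, as the table shows.

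Fourth, a reader might infer that ORR by CR status carries no information at all. The non-CR row does give the CRi, nPR and PR rate; it is redundant rather than misleading.

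Finally, a landmark has its own cost in a trial of 17 patients, since early events drop out of the summary.

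**Conclusion.** The point holds, at low priority. As planned, the EFS summary by CR status is biased in favour of CR. The direction follows from the definitions and does not depend on the exponential shape. The size does: about 0.45 to 0.75 as a rate ratio under no true association, for median EFS of 46.8 to 156 weeks, confirmation at weeks 17 to 38, a 50% CR share among those event-free at confirmation, and three years of follow-up. ORR by CR status adds nothing to the overall ORR and CR rates.

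A reader might go further and infer that the analysis would show longer EFS with CR whatever the truth, that it inflates a false-positive rate, or that it will be used to justify CR as the target of a later trial. The documents support none of these. With about 17 patients, chance could mask or reverse the artefact in the observed curves. No test is planned, so there is no error rate to inflate. Sections 13.4.1 and 13.5 tie the next step to the number of CRs only. The primary CR test, the sample size and the 7-of-17 rule are untouched.

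**What to change.** Replace the sentence in section 13.4.3 with:

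> EFS by CR status will be summarized descriptively from a fixed landmark set after the C7D1 confirmation window closes (e.g. C11D1, day 287 after first dose). Patients event-free and under follow-up at the landmark are grouped by CR status confirmed by that date, and EFS is measured from the landmark. A Simon-Makuch display with CR as a time-dependent state, which also uses later CRs, will accompany it.

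Delete ORR by CR status.

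C11D1 is 7 + 10×28 = 287 days (week 41), after the C7D1 window ends near day 266, and is already a scheduled visit. C10D1 (day 259) would fall just before that window closes and could class some C7D1 responders as non-CR.

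The cost is SAP wording and modest programming, with no new data or visits. Patients with an event before the landmark leave the landmark summary. Under the 70.1% at 24 weeks anchor, 0.701^(41/24) = 0.545 remain, about 9 of 17; with a median of 156 weeks, 0.5^(41/156) = 0.833 remain, about 14 of 17. CRs confirmed after the landmark count as non-CR in it, which is the reason for the Simon-Makuch display.
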